## **PROCEDURE or DESCRIPTION OF THE STUDY**

### **1. Workplan**

All the tests (BASC, MoCA, PANSS and EEG) will be carried out with the 47 patients with SMD to find out their baseline status. The people with SMD will be randomly assigned to an experimental group (dance therapy program) or a control group (without intervention in dance therapy but with regular pharmacological treatment). The study will last approximately 1 year between the administration of tests, the program and the analysis of results. The dance therapy program will last 20 sessions over 10 weeks. The sessions will take place at the headquarters of the Asociación Canaria de Terapias Creativas (ASCATEC) in the Siglo XXI space in Santa Cruz de Tenerife.

The 26 people with SMD in the experimental group will participate in a 10-week intervention program with 2 sessions per week in which they will work for 1 hour on memory, attention and executive functions through dance and movement, ending with 10 minutes of Mindfulness.

The 21 people in the control group will not receive any type of dance therapy intervention, but will continue with their usual pharmacological treatment.

The effects will be measured after a treatment of 20 sessions (twice a week). Results will be obtained by analyzing EEG parameters (EEG amplitude and frequency) and cognitive functions (BACS and MoCA). On the other hand, at the end of the 20-session program, tests will also be administered to assess the symptomatology of the severe mental disorder suffered by the person (PANSS) to assess the effects of the program on these variables.

### **2. Study variables (primary and secondary)**

All the data that the neuropsychological tests allow us will be collected in the intervention and control group. For the data analysis of the tests that will be administered, a series of parameters related to the objective of our study will be analyzed. In relation to the main variables, the following will be evaluated: cognitive functions, especially memory and executive functions.

An analysis of personal and sociodemographic data (age, diagnosis, medication and duration of the disease) will also be carried out.

In relation to the electroencephalogram (EEG), the following variables will be considered:

- 1) Dominant frequency: It can be analyzed whether the dominant frequency of the brain waves recorded in the EEG, such as alpha frequency (8-13 Hz) and beta frequency (12-25 Hz), show significant changes before and after the dance therapy.
- 2) Wave amplitude: the amplitude of the waves in the different regions can be observed to identify if delta, theta, alpha and beta vary with dance therapy.

In relation to the secondary variables, the PANSS tool will be administered to evaluate the impact of the program on the positive, negative and general symptoms presented by the participants, related to the disorder they suffer from.

Collecting data on these variables before and after the dance therapy intervention will allow us to assess in more detail whether the therapy has a positive impact on brain activity, cognitive functions, as well as symptoms related to the disorder.

### **3. Data Collection**

The tests will be administered after randomization and before starting the intervention to measure the basal state of each participant and after the completion of the dance therapy program in order to determine the changes generated with the dance therapy program. The tests will also be repeated after 3 months as a follow-up of the results obtained.

All registrations will be done anonymously, assigning each person an identification number. All data will be kept for 5 years.

- **Brief assessment of cognition in schizophrenia (BACS)** (Keefe et al., 2004): serves to quantify cognitive impairment in schizophrenia and/or psychosis. The BACS includes assessments of verbal memory, working memory (Digit Stream), motor speed (Token Motor), verbal fluency, attention and processing speed (Symbol

Coding), and executive function (Tower of London). The minimum and maximum scores on the BACS for each subtest are:

1. Token Motor Task (TMT): The minimum score is 0, and the maximum is 100.
2. List Learning: The minimum score is 0, and the maximum is 50.
3. Digital Sequencing Task: The minimum score is 0, and the maximum is 21.
4. Semantic Fluency: The minimum score is 0, and the maximum is 40.
5. Symbol Coding: The minimum score is 0, and the maximum is 50.
6. Tower of London: The minimum score is 0, and the maximum is 21.
7. Verbal Memory: The minimum score is 0, and the maximum is 20.

These scores are used to evaluate performance on each of the BACS subtests.

Subsequently, it is common to calculate a composite score that summarizes the individual's overall cognitive performance. For the interpretation of results, see the **attached technical sheet**. In our case, all patients in the intervention group will be patients with a diagnosis of psychosis without comorbidities.

- **Montreal Cognitive Assessment (MoCA)** (Ramírez et al., 2014): it is a 30-question test that evaluates mild cognitive dysfunctions by assessing executive function and visuospatial ability, identification, short-term memory, delayed recovery, attention, language, abstraction, animal naming and orientation. The ratings range from 0 to 30 and the cut-off value to determine a normal score is >26 points. The test is administered in about 10-12 minutes.

- **The electroencephalogram (EEG):** brain wave signals will be recorded by the 14-channel Emotiv EPOC®, whose electrodes (saline sensors) are arranged at positions AF3, F7, F3, FC5, T7, P7, O1, O2, P8, T8, FC6, F4, F8 and AF4, according to the international 10-20 system. The device also has 2 reference points at positions P3 and P4.

It should be noted that EEG data collection will be carried out in the patients' resting state. The process will be detailed as follows: First, a baseline will be carried out with the EMOTIV software of 1 minute eyes open with a fixation point of some eyes on the computer screen, followed by a gap for the participant to close their eyes. and,

continued by 1 minute of data collection in resting state where the participant keeps his eyes closed.

In addition, patients will always be given the following instructions: not to speak, not to move, try to leave the mind relaxed, as well as the same room with the same lighting and tranquility conditions will be used. To finish, the following task will be carried out: a 4-minute EEG collection will be carried out in resting state with eyes open and cross fixation point on white background, followed by 4 minutes of resting state with eyes closed.

In our case, the EEG tests will be carried out at the ASCATEC headquarters and will be carried out by [name] .

- **Positive and Negative Symptom Scale (PANSS)** (Kay et al., 1987): allows monitoring the progress of symptoms in severe mental disorders through 30 items that are grouped into three main dimensions: positive symptoms, negative symptoms and general symptoms. Each item is scored from 0 (absence of symptoms) to 7 (extreme severity) points. For the Positive Scale and the Negative Scale, the results can range from 7 to 49 and for the General Psychopathology section from 16 to 112, with the lowest total score being 30 and the highest being 210. For data interpretation, refer to the **attached technical sheet**.

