## **STUDY METHODOLOGY**

### **1. Design**

A single-centre prospective randomised controlled trial will be conducted with a minimum of 47 patients with severe mental disorder (SMD) who will be randomly assigned into two groups, 1 intervention group receiving dance therapy (n=26) and 1 control group who will not receive any intervention or added treatment apart from continuing with their usual treatment (pharmacological), but will not receive intervention with dance therapy (n=21).

In summary, the groups are:

- Experimental group (n=26): people with SMD receiving dance therapy.
- Control group (n=21): people with SMD who do not receive the dance therapy intervention but do receive their usual pharmacological treatment.

Tests will be administered before the start of the study and at the end of the study, as well as 3 months after the end of the study in order to compare the results between groups.

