### **2. Study population.**

#### **a. Population characteristics**

Patients who will participate in the dance therapy program will be referred to the Canarian Association of Creative Therapies (ASCATEC) through the Mental Health Units of the Canary Islands according to a referral program of the Government of the Canary Islands. They will be selected according to the criteria listed below without distinction of age, sex, gender or type of diagnosis, as long as they meet the main diagnosis of SMD.

The assignment will be made randomly, as they will be referred by the Government of the Canary Islands (see point 6.4.1.2. Coordination between devices in the mental health network of the Mental Health Plan in the Canary Islands 2019-2023, p.179-180).

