#### **b. Inclusion criteria**

---

 [https://www3.gobiernodecanarias.org/sanidad/scs/content/d7a0d910-4973-11e9-910bf705e6f363c5/PSMC\\_completo.pdf](https://www3.gobiernodecanarias.org/sanidad/scs/content/d7a0d910-4973-11e9-910bf705e6f363c5/PSMC_completo.pdf)

The inclusion criteria are the following:

- People diagnosed with a SMD according to the DSM-V.
- Have the capacity to decide and consent.
- Be in the age range between 18 and 65 years old.
- Do not present active consumption of toxic substances (except nicotine).
- Commitment to attendance during the entire study period from December 2023 to December 2024.

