**c. Exclusion criteria**

The exclusion criteria are the following:

- Not having given their free consent to participate in the study
- Present a serious comorbid mental disorder, associated intellectual disability, history of severe brain damage or neurological disorder that may function as a confounding factor (Associated organic type disorder, borderline or lower intellectual IQ)
- Active substance abuse (except nicotine)
- Have a cochlear implant, fixed hearing aids or head plates.
- Having suffered a concussion to the head with loss of consciousness that subsequently triggered symptoms related to the pathology.
- Suffering from epileptic seizures.
- Not having the desire to participate in dance therapy sessions for any reason or to undergo EEG-type tests.
- Be currently involved and participating in another cognitive rehabilitation program.

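### The BACS section limits the intervention group to psychosis without comorbidities, contradicting the any-SMD eligibility and randomisation text, and sets no matching rule for controls

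*Combined protocol and SAP*

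**What the plan says.** The restriction appears once, at the end of the BACS description in 3. Data Collection: "In our case, all patients in the intervention group will be patients with a diagnosis of psychosis without comorbidities". It names the intervention group and is silent on controls.

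The sections that define the trial population say something else:

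- **1. Design** describes the experimental group as "people with SMD receiving dance therapy" and the controls as "people with SMD who do not receive the dance therapy intervention but do receive their usual pharmacological treatment".
- **2.a Population characteristics**, whose subject is the patients who will take part in the dance therapy programme, selects them "without distinction of age, sex, gender or type of diagnosis, as long as they meet the main diagnosis of SMD".
- **2.b Inclusion criteria** asks for "People diagnosed with a SMD according to the DSM-V".
- **2.c Exclusion criteria** removes, for all participants, those who "Present a serious comorbid mental disorder, associated intellectual disability, history of severe brain damage or neurological disorder that may function as a confounding factor".
- **1. Workplan**, under Procedure, states: "The people with SMD will be randomly assigned to an experimental group (dance therapy program) or a control group".

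Diagnosis is among the personal data to be collected and analysed (2. Study variables). It is not named as a stratification factor, nor as a covariate in the mixed models of the statistical analysis section.

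**The concern.** The plan gives two incompatible descriptions of who receives dance therapy. The conflict with 2.a is the sharpest, because both sentences concern the same patients: one makes type of diagnosis irrelevant, the other fixes it.

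If the BACS sentence is followed as written, the intervention arm holds only patients with psychosis while the control arm may hold any SMD. H1a, H1b and secondary objectives 1 and 2 all compare the arms. A difference between diagnoses in practice effects or in natural course, over the 10-week programme and the 3-month follow-up, could then not be separated from an effect of dance therapy. The hypotheses also speak of people with SMD in general, whereas the treated patients would represent psychosis only.

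The listed non-parametric tests are unadjusted, so they would not correct for this. A covariate could not fully correct it either: with no treated patient outside psychosis, the effect of dance therapy in the other diagnoses cannot be estimated.

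**Working it through.** **1. The passages side by side**

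| Item | Intervention arm | Control arm |
|---|---|---|
| Design | SMD | SMD |
| 2.a Population characteristics | any type of diagnosis within SMD | not addressed separately |
| 2.b Inclusion criteria | any DSM-V SMD | any DSM-V SMD |
| 2.c Exclusion criteria | no serious comorbid mental disorder | no serious comorbid mental disorder |
| Workplan | randomised from one SMD pool | randomised from the same pool |
| 3. Data Collection (BACS) | psychosis, no comorbidities | nothing stated |

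The arms part only in the last row. On comorbidity, what separates that row from 2.c is the step from no serious comorbidity to none. The material difference is psychosis against any SMD.

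**2. Can randomisation produce a psychosis-only intervention arm?**

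The plan gives no figure on this point to reproduce. The inputs are the arm sizes in Design: 26 intervention and 21 control, 47 in total. The number k of enrolled patients without psychosis is not given, so it is varied as an assumption. Under random assignment to 26 and 21, the probability that all k fall among the controls is

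P(k) = C(21, k) / C(47, k).

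| k (assumed) | Share of 47 | Share of the 21 controls if all k fall there | P(k) |
|---|---|---|---|
| 0 | 0% | 0% | 1 |
| 2 | 4% | 10% | 210 / 1,081 = 0.19 |
| 5 | 11% | 24% | 20,349 / 1,533,939 = 0.013 |
| 7 | 15% | 33% | 116,280 / 62,891,499 = 0.002 |
| 10 | 21% | 48% | 352,716 / 5,178,066,751 = 0.00007 |

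With k at 0 the sentence is true automatically. With k at 2 it could come true by chance. From about k = 5 upward, a psychosis-only intervention arm is not a credible result of randomising one pool.

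**3. Can a bias be sized?**

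For an unadjusted comparison, bias = q × d. Here q is the share of controls without psychosis and d is the difference between diagnoses, in SD units, in whatever is compared. The documents give neither. The standard error of the arm difference is √(1/26 + 1/21) = 0.293 SD. Two sets of assumed inputs, with q from 0.2 to 0.5 in both, show how far the answer depends on d:

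- *Comparing outcome levels, d from 0.3 to 0.7:* bias runs from 0.2 × 0.3 = 0.06 to 0.5 × 0.7 = 0.35 SD. A two-sided 5% test (noncentral t, 45 df) would reject a true null 5.5% to 21% of the time.
- *Comparing change from baseline, d from 0.05 to 0.2:* bias runs from 0.2 × 0.05 = 0.01 to 0.5 × 0.2 = 0.10 SD. The rejection rate is 5.0% to 6.3%.

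Direction matters as well. For a one-sided 5% test, the sidedness used in the sample size calculation, a bias of 0.35 SD gives a false finding in favour of dance therapy 32% of the time if it runs that way and 0.2% if it runs the other way. In the second case it would hide a benefit. Nothing in the documents chooses among these cases.

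**The case against.** The best reply is that the sentence is descriptive and is not an allocation rule. It closes a paragraph on interpreting BACS scores and stands outside the eligibility sections. The sections that govern selection and assignment give both arms the same any-SMD rule. It may be a loose remark about the whole sample: the BACS is itself described as a measure for schizophrenia and/or psychosis, and the control-group planning values come from a dance therapy study in schizophrenia. This stands as a possible reading, though no section states it. It also does not remove the problem: if everyone is meant to have psychosis, then Design, 2.a, 2.b and the hypotheses misdescribe the population.

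A reader might go further and infer that the sentence can be met only by placing patients by diagnosis, or by removing patients without psychosis from one arm after assignment. The documents do not support that. The sentence is also met if all or nearly all 47 patients have psychosis, and with 2 exceptions it still holds by chance about one time in five.

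Two further replies stand. The comorbidity contrast is small, because 2.c already covers both arms. And the plan measures baseline, compares before with after, and fits mixed models to repeated measurements, so a stable difference in level between diagnoses would largely cancel in an analysis of change; a difference in change would not.

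**Conclusion.** The contradiction is certain: it rests on the text alone and survives every reply above. The plan does not say whether the psychosis restriction covers both arms, one arm or neither, and it must say so before patients are randomised.

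The threat to the between-arm comparison is conditional. It arises if the sentence is applied literally and the pool includes more than a very few patients without psychosis. In that case the arms would differ in diagnosis as well as in dance therapy. The probabilities of 0.19 (k = 2) and 0.013 (k = 5) assume genuine random assignment to 26 and 21; k itself is unknown.

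It would be too strong to conclude that the trial is designed with unlike arms, or to attach a particular bias to it. The ranges in the working come from assumed inputs, and the documents fix neither the size nor the direction.

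**What to change.** Reconcile Design, 2.a, 2.b, 2.c, Workplan and the BACS paragraph so that one diagnostic and comorbidity rule covers both arms and is applied before randomisation. There are two ways:

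- **(a) Psychosis only.** Move the restriction, including whatever is meant by absence of comorbidities, into 2.b and 2.c for all participants. State the hypotheses and conclusions for psychosis. The cost is a narrower referral pool and a narrower claim.
- **(b) Any SMD.** Delete the BACS sentence, keep every SMD diagnosis eligible in both arms, and enter diagnosis (psychosis yes or no) as a covariate in the mixed model. Diagnosis is already collected, so the cost is one model term. Stratifying the randomisation by diagnosis is optional, since unstratified randomisation is valid.

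Under either option, add a sentence that no patient is allocated to an arm, or removed from one, because of diagnosis. Neither option by itself changes the stated sample size. Both are changes of wording, cheap before enrolment, whereas a difference in diagnosis between arms cannot be undone after allocation.

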## **ETHICAL AND CONFIDENTIALITY ASPECTS**

The study will be conducted in accordance with the principles of the Declaration of Helsinki adopted by the 18th World Medical Assembly, Helsinki, Finland in 1964 and amended in Tokyo (1975), Venice (1983), Hong Kong (1989), South Africa (1996), Edinburgh (2000), Washington (2002), Tokyo (2004), Seoul (2008), Brazil (2013); and the Laws and Regulations in force in Europe and Spain. On the other hand, with the objective of regulating, with full respect for human dignity and identity and the rights inherent to the person, biomedical research and, in particular, research related

---

PhD in Health Sciences, Neuroscience. University of La Laguna, Spain. Master's Degree in Cognitive Neuroscience and Specific Needs for Educational Support. University of La Laguna, Spain.

to human health that involves invasive procedures, the study is will be in accordance with Law 14/2007, of July 3, on Biomedical Research.

The patient must provide consent before being admitted to the clinical study. The doctor must explain the nature, purposes and possible consequences of the study, in a way that is understandable to the patient. The information provided by the doctor must also be recorded.

For the acquisition of electroencephalography (EEG) data, informed consent will also be provided with meticulousness and rigor, both in the intervention group and in the control group, in order to guarantee the ethics and legality of the study, as well as to respect the rights and integrity of the participants. To this end, prior to inclusion in the EEG study, each participant will be given an informed consent document that exhaustively details the following aspects:

Purpose of the EEG: a clear and precise explanation will be provided about what an electroencephalogram is and its usefulness in research, in this case, to understand the influence of dance therapy on cognitive functions.

Voluntariness: it is highlighted that participation in the study is completely voluntary and that the EEG data will be collected confidentially (code instead of name in the generated database).

Right to interrupt: participants will be made aware that, at any time during the EEG, they have the right to interrupt the test if they wish.

EEG Procedure: A detailed description of the test procedure will be given, including how the electrodes will be applied to the scalp, hygiene and safety regulations and standards, and the estimated duration of the test.

Prior recommendations: Recommendations will be provided before undergoing the EEG, such as informing about the use of cochlear implants, ensuring that you have rested adequately the night before, and disclosing taking medications, especially anticonvulsants, that may affect brain activity.

Crucial Test Day Communications: Collect any relevant information on the day of the test, such as changes in health, taking additional medications, or any other circumstances that may influence the quality of the data collected.

In order to guarantee the confidentiality of the data of the patients participating in the study, only the researcher and his team of collaborators, the representative of the promoter who will carry out the monitoring tasks, the auditor in case the study was subject to an audit, the CEIm and the Health Authorities.

Rigorous application of EEG informed consent ensures that participants are properly informed and that their participation in research is carried out ethically, respecting their rights and well-being.

The study participant will give his or her consent by signing the corresponding model, which must also bear the signature of the researcher.

A copy of the informed consent model is attached.

The researcher will not initiate any investigation corresponding to the study until the patient's consent has been obtained.

The treatment, communication and transfer of personal data of all participating subjects will comply with the provisions of Organic Law 3/2018, of December 5, on the Protection of Personal Data and guarantee of digital rights, and the application of Regulation (EU) 2016/679 of the European Parliament and of the Council of April 27, 2016 on Data Protection (RGPD).

